## 6 Statistical Considerations

## **6.1 Primary Endpoint**

CO validated sustained abstinence rates at 24-weeks post baseline assessment/enrolment.

## 6.2 Secondary Endpoints

- CO validated sustained abstinence rates at 4, 12 and 24 weeks post
- 7-day point prevalence abstinence at 4, 12 and 24 weeks
- 50% Smoking reduction in participants who did not achieve full abstinence at 24 weeks
- Changes in the frequencies of risky smoking practices from baseline to 4, 12 and 24 weeks
- Adverse reactions
- Cost-effectiveness of the interventions over the 24 week trial period.

Abstinence at 4 weeks after TQD would be defined as a self-report of no smoking of conventional cigarettes (not a puff) for the previous 2 weeks, validated by a CO reading of <8ppm. Participants who do not provide a CO reading at Week 4 will be considered to be smoking. 12 and 24 week sustained abstinence will be calculated in accordance with the Russell Standard [50] as a self-report of smoking no more than 5 cigarettes since 2 weeks post-TQD validated by CO readings < 8ppm. Participants lost to follow-up or not providing biochemical validation will be included as non-abstainers.

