## Statistical Methodology and Analysis

Sustained CO validated smoking cessation at 24-weeks using the Russell Standard for cessation trials and intention to treat analysis (i.e. no more than 5 cigarettes since 2 weeks post target quit date [TQD] validated by expired CO <8ppm.Participants lost to follow-up are treated as non-abstainers. Abstinence rates and rates of those sustaining a 50% or greater reduction in baseline cigarette consumption and CO levels will be compared between the study arms. Reductions in the frequency risky smoking practices will be compared between study arms. Frequency of adverse reactions will be compared between arms.

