## **Secondary Objectives -**

- 1. Among those who have not achieved full abstinence, to compare the number reporting at least fifty percent smoking reduction at 24 weeks in the EC versus the UC arm.
- 2. To compare the number achieving 7-day point prevalence quit rates at 4-, 12- and 24-week follow-up in the EC versus the UC arm.
- 3. To document changes in risky smoking practices (e.g., sharing cigarettes, smoking discarded cigarettes) from baseline to 4-, 12- and 24-weeks in both EC and UC arm.
- 4. To determine the cost-effectiveness of the intervention
- 5. To document fidelity of intervention implementation; mechanisms of change; contextual influences and sustainability.

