## 4.6.2 Secondary Outcomes

Fifty percent smoking reduction from baseline to 24 weeks; 7-day point prevalence quit rates at 4, 12 and 24 weeks; changes in the frequencies of risky smoking practices (e.g., sharing cigarettes, smoking discarded cigarettes) from baseline to 4, 12 and 24 weeks; cost-effectiveness of the intervention; fidelity of intervention implementation; mechanisms of change; contextual influences and sustainability

[figure not shown]

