## 6.3 Sample Size

Our sample size is based on our feasibility trial. For, 0.05 alpha (two-tailed), 90% power, and cluster size of 15 participants (the feasibility study average in day centres (5)), this trial requires 240 participants per arm and 16 clusters per arm (480 participants and 32 clusters in total) to detect a difference of 5.75 between arms (i.e. 6.25% vs 0.5% respectively in the EC vs UC arms). The intraclass correlation coefficient (ICC) was set at 0.01 assuming equal cluster sizes. A final sample of 480 provides 90% power if the cluster size was smaller (n = 12) or greater (n=18) than the planned 15 participants per cluster.

There is sufficient power to detect more modest differences with smaller cessation rates in the EC arm; for example, with 5% cessation rate in the EC arm (vs. 0.5% UC), allowing 81% power with an ICC of 0.01 and 74% with an ICC of 0.025.

Sensitivity sample size calculations were conducted for the secondary outcome measuring 50% CO reduction, as previous studies have shown that CO reduction is a good predictor of future successful smoking quit attempts (20). If we assumed a minimally clinical important difference (MCID) to be 10% (i.e. 13% EC vs. 3% NRT), for 90% power, ICC = 0.01, alpha = 0.05 (two-tailed) and cluster size 15, we would need 360 participants across 24 clusters in total.

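### The 50% smoking reduction outcome has two different populations in the protocol, and the restricted one (non-abstainers only) gives a between-arm comparison that randomisation does not protect

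*Protocol*

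**What the plan says.** The protocol states the reduction outcome in five places, and they do not agree.

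- **Secondary objective 1** (synopsis and Section 2.1): "Among those who have not achieved full abstinence, to compare the number reporting at least fifty percent smoking reduction at 24 weeks", EC versus UC. This is a comparison of arms within the non-abstainers.
- **Section 6.2**: "50% Smoking reduction in participants who did not achieve full abstinence at 24 weeks". Same restriction.
- **Section 4.6.2**: "Fifty percent smoking reduction from baseline to 24 weeks". No restriction.
- **Synopsis, Statistical Methodology and Analysis**: "rates of those sustaining a 50% or greater reduction in baseline cigarette consumption and CO levels will be compared between the study arms". No restriction, and CO levels are added to cigarette consumption.
- **Section 6.3**: a supporting sample size for a 50% reduction measured by CO, with a minimally important difference of "10% (i.e. 13% EC vs. 3% NRT". The calculation removes no quitters.

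For the primary outcome, Section 6.3 plans on "6.25% vs 0.5% respectively in the EC vs UC arms". Section 6.2 counts participants who are lost to follow-up, or who give no biochemical validation, as non-abstainers. It gives no rule for their reduction status.

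**The concern.** Whether a participant belongs to the non-abstainer group is known only after allocation, and it is decided by the outcome that the trial expects EC to change. Restricting to that group takes out mostly EC participants. If they are people who would otherwise have cut down substantially, the EC arm loses likely reducers and the UC arm does not. The difference in reduction among those left then mixes any effect of EC on continuing smokers with a difference in who is left.

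Two things are at stake. The first secondary objective could understate a real benefit, or in some circumstances show the wrong sign. And because two sections state the outcome unrestricted, two analysis populations are available for one outcome, and the protocol does not say which governs. An analysis plan could only follow one statement and contradict the other.

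Objective 1 also speaks of the number reporting a reduction and fixes no denominator. If all randomised participants were the denominator, quitters would count as failures on reduction, which pushes in the same direction.

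**Working it through.** **Inputs from the protocol (Section 6.3).** Quit rates qE = 6.25% and qU = 0.5%; reduction rates 13% and 3%; two-sided alpha 0.05; 90% power; ICC 0.01; cluster size 15; 240 participants per arm.

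**Reproducing the plan's own figures.** The method is the pooled two-proportion formula without continuity correction, times the design effect 1 + (15 − 1) × 0.01 = 1.14, rounded up to whole clusters.

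- 13% versus 3%: 153 × 1.14 = 174.4 per arm, so 12 clusters per arm and 360 in total. This matches "for 90% power, ICC = 0.01, alpha = 0.05 (two-tailed) and cluster size 15, we would need 360 participants across 24 clusters in total".
- 6.25% versus 0.5%: 206 × 1.14 = 234.8 per arm, so 16 clusters per arm and 480 in total. This matches "this trial requires 240 participants per arm and 16 clusters per arm".

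The sample sizes are sound. The question is only the analysis population.

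**Who is removed.** Non-quitters: EC 240 × 0.9375 = 225; UC 240 × 0.995 = 238.8, about 239. So about 15 leave EC and about 1 leaves UC.

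**Formulas.** Let r be the share of all randomised who reduce by at least 50% without quitting.

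- Restricted rate = r / (1 − q).
- Composite rate = q + r, in all randomised.

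**Using the protocol's 13% and 3%.** The text does not say whether these include quitters.

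- *Including quitters:* EC (13 − 6.25) / 93.75 = 7.2%; UC (3 − 0.5) / 99.5 = 2.5%. The difference falls from 10 to 4.7 points. Power is about 60% with 225 versus 239, against 96.8% for 13% versus 3% with 240 per arm (design effect 1.14 in both).
- *Excluding quitters, as shares of all randomised:* EC 13 / 93.75 = 13.9%; UC 3 / 99.5 = 3.0%.
- *Read directly as rates among non-quitters:* power with 225 versus 239 is 96.3%.

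**When the sign can change.** The UC reduction rate among all randomised is not given for this endpoint, so it is an assumption here, varied from 10% to 40%. Let f be the share of the extra quitters (6.25 − 0.5 = 5.75 points) who would have been reducers under UC, with no other EC effect. The EC restricted rate is then (r − f × 5.75) / 93.75, with r in per cent.

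| UC r | f | EC restricted | UC restricted | Difference | Composite, EC − UC |
|---|---|---|---|---|---|
| 10% | 1 | 4.5% | 10.1% | −5.5 | 0 |
| 20% | 1 | 15.2% | 20.1% | −4.9 | 0 |
| 30% | 1 | 25.9% | 30.2% | −4.3 | 0 |
| 40% | 1 | 36.5% | 40.2% | −3.7 | 0 |
| 10% | 0.5 | 7.6% | 10.1% | −2.5 | +2.9 |
| 20% | 0.5 | 18.3% | 20.1% | −1.8 | +2.9 |
| 30% | 0.5 | 28.9% | 30.2% | −1.2 | +2.9 |

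Break-even: setting the two restricted rates equal gives f = r / (1 − qU). With no other EC effect, the comparison turns against EC only when f exceeds the UC restricted rate (10.1% at r = 10%, 30.2% at r = 30%).

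**Adding a direct effect.** At r = 20% and f = 0.5, let EC also move 5% of all randomised to reduction. The restricted rates are (20 − 2.875 + 5) / 93.75 = 23.6% versus 20.1%, a difference of +3.5 points. The composite is 6.25 + 22.125 = 28.4% versus 20.5%, a difference of +7.9 points.

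**The case against.** The strongest reply is that the protocol's own figures do not show harm. With 13% versus 3% the restricted comparison favours EC on every reading. If the UC reduction rate were really 3%, the f = 1 scenario could not occur, since 5.75 points of quitters cannot come out of 3 points of reducers. Those rates are an imperfect guide, because they refer to CO reduction and label the comparator NRT, but they are the only ones in the document. A reader might infer that the restricted analysis will make EC look harmful. The documents do not support that: it needs an assumed UC rate, and no worthwhile EC effect on continuing smokers, whereas Section 6.3 plans around a 10-point reduction difference.

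A reader might also infer that the bias must grow as EC produces more quitters. It need not. If the extra quitters come from would-be reducers in proportion to the base rate, the restricted rates are equal at any quit rate.

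The scale is also modest. At a 15% rate (assumed), the standard error of the difference is √(0.15 × 0.85 × (1/225 + 1/239) × 1.14), about 3.5 points, so the tabulated deficits would often not reach significance.

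Finally, Section 4.6.2 may simply be an abbreviated list, and reduction among continuing smokers is a fair question in its own right.

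All of this limits the size and certainty of the problem, and it stands. It does not make the restricted comparison a randomised one. An abbreviated list also does not explain the synopsis statistics, which compare reduction rates between the arms with no restriction. And interest in continuing smokers can be met by description.

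**Conclusion.** The point holds as a risk of bias or dilution in one secondary outcome, together with an inconsistent definition of its population. It does not hold as a prediction that EC will look harmful, nor as a claim that the protocol restricts the comparison throughout.

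On the protocol's figures, the restriction either cuts a 10-point difference to 4.7 points (if 13% and 3% include quitters) or leaves a clear EC advantage (if they do not). A reversed sign, of about 1 to 5.5 points in the scenarios examined, requires an assumed UC reduction rate of 10% to 40%, extra quitters drawn disproportionately from would-be reducers, and little EC effect on continuing smokers. A moderate direct effect restores the sign, but the restricted difference can still understate the benefit seen in all randomised participants. The primary analysis and its conclusion are not affected.

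**What to change.** Make the between-arm comparison at least 50% reduction from baseline or abstinence at 24 weeks, in all randomised participants, with missing counted as failure. That rule also settles the status of participants lost to follow-up, which matters because Section 1.2 describes feasibility retention only as above 50%.

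Report the three-way split (abstinent, reduced by at least 50%, neither) by arm, and reduction among continuing smokers, as description without a between-arm test.

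Align the synopsis objective, the synopsis statistics, and Sections 2.1, 4.6.2, 6.2 and 6.3 on the population and on whether reduction is measured by cigarettes, CO or both. In Section 6.3, state whether 13% and 3% include quitters, and reconcile the NRT label with the UC comparator. If they are composite rates, the 360 stands and the planned sample gives about 97% power.

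The cost is a wording amendment, with no new data and no change in sample size. The downside is that the composite partly overlaps the primary outcome; the descriptive split shows how much of any difference is quitting and how much is reduction.

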## 6.3 Sample Size

Our sample size is based on our feasibility trial. For, 0.05 alpha (two-tailed), 90% power, and cluster size of 15 participants (the feasibility study average in day centres (5)), this trial requires 240 participants per arm and 16 clusters per arm (480 participants and 32 clusters in total) to detect a difference of 5.75 between arms (i.e. 6.25% vs 0.5% respectively in the EC vs UC arms). The intraclass correlation coefficient (ICC) was set at 0.01 assuming equal cluster sizes. A final sample of 480 provides 90% power if the cluster size was smaller (n = 12) or greater (n=18) than the planned 15 participants per cluster.

There is sufficient power to detect more modest differences with smaller cessation rates in the EC arm; for example, with 5% cessation rate in the EC arm (vs. 0.5% UC), allowing 81% power with an ICC of 0.01 and 74% with an ICC of 0.025.

Sensitivity sample size calculations were conducted for the secondary outcome measuring 50% CO reduction, as previous studies have shown that CO reduction is a good predictor of future successful smoking quit attempts (20). If we assumed a minimally clinical important difference (MCID) to be 10% (i.e. 13% EC vs. 3% NRT), for 90% power, ICC = 0.01, alpha = 0.05 (two-tailed) and cluster size 15, we would need 360 participants across 24 clusters in total.

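### The 50% reduction outcome is defined differently in the synopsis, objectives, outcome lists, Table 1 and sample size section, so the 360-participant, 24-cluster calculation is not tied to the endpoint listed in 6.2

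*Protocol*

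**What the plan says.** The protocol describes a 50% reduction outcome in six places:

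- **Section 2.1, secondary objective 1 (also in the synopsis objectives):** participants reporting at least a 50% reduction in smoking at 24 weeks, among those not fully abstinent.
- **Section 4.6.2:** a 50% reduction in smoking from baseline to 24 weeks, with no restriction to non-abstainers.
- **Table 1 (section 4.9):** 50% smoking reduction marked at 4, 12 and 24 weeks.
- **Section 6.2:** "50% Smoking reduction in participants who did not achieve full abstinence at 24 weeks".
- **Synopsis, Statistical Methodology and Analysis:** a between-arm comparison of "rates of those sustaining a 50% or greater reduction in baseline cigarette consumption and CO levels".
- **Section 6.3:** "Sensitivity sample size calculations were conducted for the secondary outcome measuring 50% CO reduction", with assumed rates "i.e. 13% EC vs. 3% NRT", and the result that "we would need 360 participants across 24 clusters in total".

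The control arm in section 4.4 is usual care: very brief advice and signposting to the local stop smoking service. The trial size of 480 participants in 32 clusters comes from the abstinence endpoint in the first paragraph of section 6.3.

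**The concern.** The descriptions differ on three things that decide the result: the measure (cigarettes, CO or both), the denominator (all participants or non-abstainers only) and the timing (24 weeks, a sustained criterion, or three visits). An analysis plan that follows one of them departs from another.

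Two consequences matter. First, participants know what they were given, so reported consumption and expired CO may not agree, and the choice of measure could change the conclusion. Second, non-abstainers are a subgroup formed after randomisation. The plan expects the arms to differ in abstinence (6.25% vs 0.5%), so this denominator is expected to differ in composition by arm, and a comparison within it is not protected by randomisation.

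Section 6.3 adds a labelling problem. It calls CO reduction the secondary outcome, although CO reduction alone is in neither 2.1, 4.6.2 nor 6.2, and it names a comparator that the trial does not have.

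**Working it through.** **1. The definitions side by side**

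| Place | Measure | Denominator | Timing |
|---|---|---|---|
| 2.1, objective 1 | Reported smoking | Non-abstainers | 24 weeks |
| 4.6.2 | Smoking | No restriction stated | Baseline to 24 weeks |
| Table 1 | Smoking | Not stated | 4, 12 and 24 weeks |
| 6.2 | Smoking | Non-abstainers | 24 weeks |
| Synopsis, statistical paragraph | Cigarettes and CO | No restriction stated | Sustained |
| 6.3 | CO alone | Not stated | Not stated |

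Only objective 1 and 6.2 share a denominator. The CO-only measure of 6.3 appears nowhere else.

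**2. Reproducing the plan's figure**

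Inputs from section 6.3: 13% vs 3%; "for 90% power, ICC = 0.01, alpha = 0.05 (two-tailed) and cluster size 15".

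- Pooled two-proportion formula without continuity correction: n per arm = [1.960 × √(2 × 0.08 × 0.92) + 1.282 × √(0.13 × 0.87 + 0.03 × 0.97)]² / 0.10² = 152.6.
- Design effect: 1 + (15 − 1) × 0.01 = 1.14.
- 152.6 × 1.14 = 173.9 per arm; 173.9 / 15 = 11.6, rounded up to 12 clusters per arm.
- 12 × 15 × 2 = 360 participants in 24 clusters.

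This matches. Changing the label NRT to UC does not alter it, because the rates stay the same.

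**3. What the definition does to power at 480 (illustration)**

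The protocol gives no rates for the cigarette-based or non-abstainer versions. The cases below carry the 13% and 3% over as an assumption, keep the design effect at 1.14 and use the pooled two-sided test at 0.05.

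- **Case A: 13% vs 3% in all randomised.** Effective n = 240 / 1.14 = 210.5 per arm. Power is about 97%.
- **Case B: 13% vs 3% already refers to non-abstainers.** At the planning quit rates, 240 × 0.9375 = 225 (EC) and 240 × 0.995 = 238.8 (UC) remain. Power is about 96%.
- **Case C: 13% vs 3% includes every planned quitter, and the analysis is restricted to non-abstainers.** EC: (0.13 − 0.0625) / 0.9375 = 7.2%. UC: (0.03 − 0.005) / 0.995 = 2.5%. With 225 and 238.8 remaining, power is about 60%. At a total of 360 it would be about 48%.

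The difference shrinks from 10 points to about 4.7 in case C because removing quitters takes more successes out of the EC arm than out of the UC arm.

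**The case against.** The best defence is that little rests on this calculation. Section 6.3 presents it as a sensitivity calculation, 480 exceeds 360, and NRT may simply be a slip for UC. Section 6.4 has the analysis plan reviewed by an independent statistician, finalised before data collection is complete and agreed with the TSC, which limits any choice of definition after results are known. All of this stands, and it keeps the point at the level of endpoint definition and labelling. It does not settle the conflict, because the protocol states several versions and does not leave the choice open.

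A reader might go further and infer that 360/24 relates to nothing the trial will compare. The documents do not support that: the synopsis plans a between-arm comparison that involves CO. The accurate statement is that this comparison is described as sustained and pairs CO with cigarettes (one joint criterion or two comparisons; the wording allows both), and that it is neither the CO-only outcome of 6.3 nor the 6.2 endpoint.

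A reader might also take 60% as the trial's actual power for the 6.2 endpoint. It is not. It needs 13% and 3% to include all planned quitters, and CO-based rates to hold for a smoking-based endpoint. The protocol says neither, and it claims no power for the 6.2 endpoint.

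**Conclusion.** The point holds as an inconsistency in endpoint definition. The reduction outcome differs across the protocol in measure, denominator and timing; CO reduction alone is in no objective or endpoint list; and NRT is not a trial arm. The 360/24 figure is correct for its stated inputs and has no bearing on the 480, but the protocol does not say which version of the outcome it supports.

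The range of about 60% to 97% power at 480 shows that the choice of definition matters. It is an illustration under the assumptions listed with each case, and the true power for the 6.2 endpoint cannot be computed from the protocol. The correction should be made, but the primary endpoint and the trial size are unaffected.

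**What to change.** - Adopt one measure, one denominator and one time point, and use them in the synopsis, 2.1, 4.6.2, Table 1, 6.2 and 6.3.
- Preferably compare all randomised participants at 24 weeks, with CO as the objective component. The non-abstainer comparison can stay as a descriptive result.
- In 6.3, replace NRT by UC, or state why a 3% rate under NRT is a proxy for UC.
- In 6.3, say which definition and population the 13% vs 3% and the 360/24 refer to. If the chosen definition is a different one, give its assumed rates and restate the figure.

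Cost: wording, possibly one recalculated figure, and a small change to a secondary objective if the denominator becomes all randomised. No new data are needed, since Table 1 already has CO and smoking behaviour at baseline and every follow-up.

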## 6.4 Statistical Analysis

Analyses will be undertaken after the last participant has completed the 6-month follow-up.

Participants' demographic and smoking characteristics at baseline will be presented broken down by trial arms. We will present means and standard deviations for continuous measures that are approximately symmetric; median and quartiles if the distribution is skewed. Discrete outcomes will be described using both the number and proportion (percentage). Similarly, we will present summary measures of the primary and secondary outcomes.

The primary analysis will use mixed-effect model with random effects for clusters and fixed effect for treatment to compare the two arms on quit rates. The model will be adjusted for cluster-level and individual-level variables that differ between arms at baseline. The number needed to treat (95%CI) will also be estimated based on the results of the primary endpoint. The pattern of missing data by baseline characteristics will be explored. Sensitivity analyses will be conducted to assess the robustness of conclusions to missing outcome data (complete case analysis, multiple imputation) and departures from randomised treatment (per protocol analysis).

A detailed statistical analysis plan will be developed by the trial statistician and reviewed by the independent statistician. It will be finalised prior to completion of data collection and agreed with the TSC.

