## 4.9 Schedule of Assessment

Table 1: Schedule of enrolment, interventions, and assessments.

	STUDY PERIOD					
	Enrolment	Allocation	Po	st-alloca	tion	Close-out
TIMEPOINT**	Baseline	0	4- week	12- week	24- week	t x
ENROLMENT:						
Eligibility screen	Χ					
Informed consent	Χ					
Allocation		Х				
INTERVENTIONS:						
Usual care		Х				
EC		Х				
ASSESSMENTS:						
Sociodemographic characteristics	Χ					
Mental health status	Х					
CO breath sample	X		Х	Х	Х	
Smoking behaviour (incl. risky smoking practices)	Х		Х	Х	Х	
Motivation to Stop Smoking (MTSS)	Х		Х	Χ	Х	
Fagerström Test of Cigarette Dependence (FTCD)	Х		Х	Х	Х	
7-day point prevalence & 50% smoking reduction			Х	Х	Х	
Thoughts about EC	Χ		Х	Х	Х	
Adverse effects	X		Х	Х	Х	
Use of EC & unintended consequences (EC arm)			Х	Χ	Х	
EC positive effects & EC support (EC arm)			Х	Х	X	
Smoking cessation support	X		Х	X	X	
received  Health-care service use	X		Х	X	X	
Health Related Quality of Life	X		Х	X	X	
Substance use	X					
AUDIT-C	X					
Assessment of main effectiveness outcome					Х	
Debrief					Х	Х

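### The primary model adjusts for whichever variables happen to differ between arms at baseline, instead of a small covariate set fixed in advance, although only about 16 quitters are expected

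*Protocol*

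**What the plan says.** Section 6.4 defines the primary analysis: "The primary analysis will use mixed-effect model with random effects for clusters and fixed effect for treatment to compare the two arms on quit rates". It then adds the covariate rule: "The model will be adjusted for cluster-level and individual-level variables that differ between arms at baseline". It names no covariate, does not say how a difference is to be judged, and sets no maximum number. It does not name an unadjusted model, or a model with pre-specified covariates, as primary. The same section requires the statistical analysis plan to be final before data collection is complete. That does not require it to be final before baseline data by arm exist.

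The pool of candidates is wide. Table 1 in section 4.9 ("Schedule of enrolment, interventions, and assessments") marks 13 assessment rows at baseline, several of which hold more than one variable. Section 6.4 also admits cluster-level variables, which it does not list.

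Section 6.3 plans on quit rates of "6.25% vs 0.5% respectively in the EC vs UC arms" with 240 participants and 16 clusters per arm. It does not state how many quitters that implies.

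**The concern.** Adjustment helps when a covariate predicts the outcome. An observed difference between arms is another criterion. It lets in variables unrelated to quitting that differ by chance, and it leaves out strong predictors that happen to balance or fall just short of being judged different.

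The rule also leaves the primary model open. Two competent analysts could follow the sentence to different covariate sets, and neither could write the set down until they had compared the arms. With so few quitters expected, each covariate is costly, so the lack of a cap matters more here than in a trial with many events.

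**Working it through.** **Inputs.** All are from section 6.3 unless marked: two-sided alpha 0.05, power 90%, 15 participants per cluster, 240 participants and 16 clusters per arm, quit rates 6.25% and 0.5%, ICC 0.01. Under section 6.2, people lost to follow-up count as non-abstainers, so the denominator stays at 480.

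**Step 1: the plan's own figure.** Two proportions, pooled variance under the null, no continuity correction, with mean rate (0.0625 + 0.005)/2 = 0.03375:

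n = [1.960 × √(2 × 0.03375 × 0.96625) + 1.282 × √(0.0625 × 0.9375 + 0.005 × 0.995)]² / 0.0575² = 205.2, rounded up to 206 per arm.

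Design effect = 1 + 14 × 0.01 = 1.14. Then 206 × 1.14 = 234.8 per arm, and 234.8/15 = 15.7, so 16 clusters and 240 per arm. Power at 240 per arm is 90.7%. For 5% against 0.5%, power is 80.8% at ICC 0.01 and 73.9% at ICC 0.025 (stated: 81% and 74%). The sample size reproduces.

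**Step 2: expected quitters.**
- Planning rates: 240 × 0.0625 = 15.0 (EC) and 240 × 0.005 = 1.2 (UC), total 16.2.
- The protocol's 5% scenario: 12.0 + 1.2 = 13.2.

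**Step 3: events per coefficient** (treatment plus covariates, not counting the intercept or the cluster variance).

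| Covariates | 16.2 events | 13.2 events |
|---|---|---|
| 1 | 8.1 | 6.6 |
| 2 | 5.4 | 4.4 |
| 3 | 4.05 | 3.3 |

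**Step 4: how often the rule would select something by chance.** The protocol gives no criterion, so this is illustrative. Assume that a difference means p < 0.05 and that the k candidates are independent. P(at least one) = 1 − 0.95^k; expected number = 0.05k; P(three or more) is binomial.

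| k | At least one | Expected | Three or more |
|---|---|---|---|
| 10 | 40% | 0.5 | 1.2% |
| 15 | 54% | 0.75 | 3.6% |
| 20 | 64% | 1.0 | 7.5% |

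These figures depend on how the comparison is made. Centres are randomised, so baseline variables may cluster. Suppose a baseline ICC of about 0.046 (my assumption) and tests that ignore clustering. The design effect is 1 + 14 × 0.046 ≈ 1.65, and the per-variable chance is 2 × [1 − Φ(1.96/√1.65)] ≈ 13%. A simulation of 1,000 trials with 12 such variables selected at least one in 81%, 1.5 on average, with a 90th percentile of 3. The protocol does not say which situation would apply.

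**Step 5: sparse data.** P(no UC quitter) = 0.995^240 = 30%, assuming independence. No covariate enters this calculation. Covariates add to the problem: section 2.3 gives Wales and the Southwest three centres each, or 45 people. At the average rate, P(no quitter in such an area) = 0.96625^45 = 21%. If area were judged to differ and entered the model, that area's coefficient could not be estimated.

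**The case against.** The strongest defence has four parts.

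**Selection uses baseline data, never outcomes, and the rule is stated in advance.** This stands. A reader might infer that the nominal 5% error rate is lost. The documents do not support that: the percentages in step 4 are chances that a covariate is selected, not chances of a false-positive result.

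**Imbalance here need not be chance.** Section 4.3 has expressions of interest taken before centres know their allocation only where possible, and section 3.3 applies one exclusion to the EC arm alone. Recruitment could therefore create systematic differences, and adjusting for them has a rationale. This also stands, and it is a reason not to insist on a wholly unadjusted primary model, particularly as section 4.3 names no stratification factor. It does not rescue the rule, which still omits a prognostic variable whose difference goes unremarked. A prognostic covariate fixed in advance is adjusted for in either case.

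**The sparse UC arm is not caused by covariates.** Correct. The 30% chance of no UC quitter exists with treatment alone in the model, and changing this sentence does not remove it. Nor is about 4 events per coefficient the figure to expect. It needs three selected covariates, which under independent tests at p < 0.05 happens in about 1% to 8% of trials, although more often if clustering is ignored.

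**The statistical analysis plan will settle details**, with independent statistical review and agreement by the steering committee. Those safeguards are real, and a candidate list or cap could be left to that document. But the protocol states a definite rule. A plan that named its covariates would have to override it, and a plan that kept it would still let the baseline data choose the model.

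**Conclusion.** The point holds as a flaw in how the primary model is specified. The covariates are chosen by observed imbalance, without a list, criterion or cap, in a trial expected to yield about 16 quitters (15.0 EC, 1.2 UC), or about 13 in the protocol's lower scenario. What is at stake is an undetermined primary model, and a treatment estimate that an uncapped covariate set could make unstable or non-estimable.

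A reader might go further and infer an inflated error rate or an inadequate sample size. Neither follows: no type I error inflation has been shown, and the sample size reproduces.

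The event counts are expectations at the planning rates. The selection percentages rest on a p < 0.05 reading, candidate counts and (in)dependence that the protocol does not state. They illustrate the rule and do not measure it. The conclusion does not depend on them.

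**What to change.** Replace the sentence in section 6.4. The primary model should contain treatment, the random cluster effect, any factor used in randomisation, and either no further covariates or at most one or two prognostic baseline covariates already collected, such as FTCD and MTSS. Name them before any baseline comparison by arm and keep them whatever the observed balance. The cap is deliberate: two covariates already bring the expected events per coefficient down to 5.4.

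Move adjustment for observed baseline differences, including any that arise from recruitment after allocation is known, to a sensitivity analysis. The statistical analysis plan should carry the same wording.

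The cost is one changed sentence, one sensitivity analysis, no added data and no change to 480 participants. The small downside is that a chance or recruitment imbalance in an unnamed variable is then handled only in the sensitivity analysis.
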